1. PROTOCOL SUMMARY

1.1 SYNOPSIS

Title: Mobile Medication Adherence Platform for Buprenorphine-Naloxone (MAP4BUP) During Treatment of Opioid Use Disorder: Phase I MAP4BUP Study

Opioid misuse and abuse affect the health and the well-being of millions of Americans. On average, 130 Americans die every day from an opioid overdose in 2017, according to CDC data. Opioid agonist therapy, such as buprenorphine-naloxone (BUP/NAL), can reduce opioid overdose deaths, decrease opioid misuse, and improve quality of life. Unfortunately, poor medication adherence is a barrier to long term efficacy of this therapy. To assess compliance, we plan to substantially monitor adherence to inexpensive oral buprenorphine-naloxone with Pillsy, a Bluetooth-connected smart pill cap and pharmacy software platform. The technology platform was developed over the past three years using principles of behavioral science, modern design, and highly scalable wireless and mobile technologies.

We will build out and adapt our current Pillsy platform, then test it in a small-scale trial to assess feasibility, usability, and effectiveness. We propose, in Phase I, to conduct a study involving 30 subjects selected randomly among patients prescribed (BUP/NAL) for opioid misuse to better understand their willingness to use Pillsy and identify areas of problematic compliance. Using the data obtained in Phase I and after meeting with the FDA, we will further refine the platform in Phase II. This will be a collaborative study between Washington State University, Pillsy and the clinical site Ideal Option.

The purpose of this randomized, controlled trial in Phase I is to determine whether the Pillsy intervention can improve adherence to BUP/NAL compared to services as usual (SAU). The primary endpoint will be adherence to MAT as determined through the medication possession ratio at the end of the trial. The hypothesis is that the Pillsy intervention will significantly improve adherence to medication-assisted treatment (MAT) compared with SAU.

Study Design

Narrative Study Description

The research coordinator (RC) will provide the Pillsy device and orient the participants in the use of the Pillsy app. Participants in both groups will also have full access to services normally provided by the prescribing office including blood testing and counseling services (i.e. SAU). All participants will receive the Pillsy cap (to track and time stamp pill bottle openings, closings, etc). The participants assigned to the Pillsy intervention, will also have a mobile phone reminder application. If the participant does not take their medicine at the correct time, a light on the smart pill cap will flash. If the bottle is not opened within 20 minutes, the Pillsy app sends an SMS text message to participant's phone. If the bottle is not opened within 60 minutes, the participant then receives an automated phone call. The participant may also receive brief motivational phrases or craving surveys that can be tailored to participant needs and preferences.

Pillsy also includes a Pillsy Helpers feature in which the participant can name friends and family members who will also receive a text message notification one hour after a missed dose. If the participant is struggling, his or her social support can attempt to contact the participant. The MAT prescriber may also be a Pillsy Helper. The MAT prescriber may be contacted when the participant has missed a dose if they are designated as a helper, giving the prescriber the opportunity to intervene. Providers may decide to call the imminently nonadherent participant to provide a brief, timely therapeutic intervention for which the provider can bill using the 99091 CPT code.

All data handling will conform to appropriate regulatory guidelines (HIPAA) and will be collected in such a way that it can be integrated into existing EMRs. The long-term goal is for this information to be available to one's prescriber and provider in real-time for monitoring.

Participants in SAU arm will receive a prescription for BUP/NAL tablets/sublingual films and any services normally provided by the prescribing office. Participants in SAU arm will receive an inactive Pillsy smart cap that will track openings but will not provide reminders or any other messaging.

Primary Endpoint

Adherence to BUP/NAL treatment assessed by medication possession ratio (pills taken/pills prescribed)

Secondary Endpoints

1. Participant engagement quantified through office visits and assessed via real time surveys
2. Usability and reminder feedback assessed through questionnaires
3. Participant self-report of adherence
4. Use of non-prescribed opioids

2. INTRODUCTION

2.1 STUDY RATIONALE

The United States is in the midst of an opioid epidemic. According to the Substance Abuse and Mental Health Services Administration (SAMHSA) 2016 estimates, 11.5 million people misuse their prescription opioids, 948,000 use heroin, and 2.1 million people meet diagnostic criteria for opioid use disorder (OUD). A documented 42,249 Americans died of opioid overdose in 2016, which is an average of 116 preventable deaths per day ¹. Opioid Agonist Therapy (OAT), such as buprenorphine/naloxone (BUP/NAL), can reduce opioid overdose deaths by at least 70%, decrease opioid misuse, and improve quality of life. Because of its proven efficacy, the National Institute on Drug Abuse (NIDA), the Substance Abuse and Mental Health Services Administration (SAMHSA), the American Society of Addiction Medicine (ASAM), and the American Academy of Addiction Psychiatry (AAAP) endorse the use of medication-assisted therapy in the treatment of OUD.

Poor medication adherence is one of the main barriers to long term efficacy of opioid agonist therapy (OAT). A year-long outpatient study of OAT in 225 treatment-seeking patients with opioid use disorder (OUD)² showed that treatment retention fell to under 50% by 12 weeks and only 25% of patients remained at one year. Novel depot formulations of efficacious drugs can improve adherence. However, in Ling's study, depot opioid agonists provided only a modest increase in adherence (13.8% compared to oral buprenorphine/naloxone BUP/NAL) despite the significant (565%) price increase compared to the generic drug.

To improve performance, we plan to substantially increase adherence to inexpensive oral BUP/NAL with Pillsy, a smart technology platform developed over the past three years using principles of behavioral science, modern design, and highly scalable wireless and mobile technologies. Pillsy acts like a digital medication coach, providing education and reminders using a mobile app, text messages, and automated phone calls. The platform is built around a Bluetooth-based smart pill bottle cap that automatically tracks doses, timing and sends intelligent reminders to create a unique feedback loop, which allows us to constantly optimize our incentive/reminder messages to meet user needs and increase adherence. Since its recent launch, the company has already over 1,000 clients. Pillsy can substantially increase adherence to OAT and decrease opioid-related morbidity and mortality. Since Pillsy only nominally increases the cost of oral BUP/NAL treatment and providers can bill for monitoring time (CPT code 99091), it is an attractive solution to patients, providers, and payers. However, there are few if any studies available that have systematically investigated this technology's impact on medication adherence in this population.

We will conduct a Phase I study involving 30 subjects selected randomly among patients prescribed (BUP/NAL) for opioid misuse, to better understand their willingness to use Pillsy and identify areas of resistance.

3. OBJECTIVES AND ENDPOINTS.

- 1- Compare Pillsy delivered BUP/NAL adherence to conventional BUP/NAL therapy.
- 2- Evaluate non-prescribed opioid use and therapy retention between groups.
- 3- Understand participants' willingness to use Pillsy and identify areas of resistance.

4. STUDY POPULATION

Recruitment

Goal: Enroll 30 eligible adults: 15 control group services as usual (SAU); 15 Pillsy group (PLY).

4.1 INCLUSION CRITERIA

Participants will be **eligible for inclusion** if they meet all the following criteria:

- Subject can and has signed an Institutional Review Board (IRB) approved informed consent form (ICF).
- Age ≥ 18 and up.
- Self-reported that they have been diagnosed with an OUD and are in receipt of BUP/NAL for their OUD.
- Owns a working smartphone.
- Has been prescribed BUP/NAL and is a current patient at Ideal Option.
- Able to read and speak English.
- Can identify one study partner/caregiver who agrees to participate (i.e., as described above, this "helper" can be a friend of family member, a provider, etc.).

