referred for follow-up with a RC. The RC will contact the patient and assess the participant's appropriateness for the study in a screening interview. The RC will explain the clinical study in detail and will obtain informed consent. All potential participants will be given plenty of time to read the consent form. They will have time to ask questions and their questions will be answered to their satisfaction by the study RC, the Principal Investigator, or the Co-investigator.

After ensuring the potential subject has understood his/her role in the study, then he/she will be requested to sign and date the Institutional Review Board (IRB) approved Informed Consent Form (ICF), after which a screening number will be assigned. The consenting process should be conducted at the clinic's site and in a consistent manner for every potential participant.

The consent process for this study will include a video demonstration of handling of the Pillsy cap and how the Pillsy system works to aid in the subject's and study subject partner's understanding of this technology. If the participant meets inclusion/exclusion criteria, he/she will be randomly assigned to one of the two arms of the study.

Method of Assigning Subjects to Study Arms: Randomization

Subjects will be centrally registered and randomly assigned 1:1 to the PLY or SAU group. We will use permuted block randomization and stratify on 1) age, 2) sex, and 3) severity of OUD (mild, moderate, severe) based on DSM-5 criteria for diagnosis of opioid use disorder (Mild: 2-3 symptoms. Moderate: 4-5 symptoms. Severe: 6 or more symptoms).

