If the patient does not take their medicine at the correct time, a light on the smart pill cap begins to flash. If the bottle is not opened within 20 minutes, the Pillsy application sends an SMS text reminder to the patient's phone. If the bottle is not opened within 60 minutes, the patient receives an automated phone call. The patient may also receive brief motivational phrases that can be tailored to patient needs and preferences. Pillsy also includes a "Pillsy Helpers" feature in which the patient can name friends and family members who will also receive a text message notification one hour after a missed dose. Thus, if the patient is struggling, his or her support system can attempt to contact the patient and offer motivation. Importantly, as proposed in the clinical trials detailed in this application, the MAT prescriber can also be a Pillsy Helper.

All data handling will conform to meet HIPAA requirements, including administrative, physical, and technical safeguards. Data will be encrypted in storage and in rest in REDCap with regularly scheduled data deposits from Pillsy into REDCap.

Participants in the service as usual (SAU) arm will receive a prescription for BUP/NAL tablets/sublingual films and any services normally provided by the prescribing office. Participants in the SAU arm will receive an "inactive" Pillsy smart cap that will track openings but will not provide reminders or any other messaging.

Screening Visit

The RC will screen the patient to assess the participant's appropriateness for the study. If the prospective participant meets inclusion/exclusion criteria, the RC will explain the clinical study in detail and informed consent will be obtained. If eligible, the participant will be trained on how to use the Pillsy system (cap and app) if randomized to PLY group. No training will be needed for the SAU. While their cap will be activated to capture open and close times, that is the only data that will be collected on the cap. and randomized to one of the study groups.

Week 1 Assessment

Study participants will return to office as frequently as the prescriber sees fit in the course of addiction treatment. At 1 week +/- 1 day, the RC will count BUP/NAL tablets/sublingual films and compare to the prescribed number of pills for that period. Participants will complete questionnaires.

Week 6 Assessment

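### The partner criterion and the pre-randomisation video may give SAU participants a study-enlisted, Pillsy-aware supporter, which could dilute the PLY–SAU contrast and would go unmeasured

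*Combined protocol and SAP*

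**What the plan says.** - **Eligibility (4.1 Inclusion Criteria).** Participants qualify "if they meet all the following criteria", and one criterion is "Can identify one study partner/caregiver who agrees to participate". The accompanying note calls this person the helper, who may be a friend, a relative or a provider. The criterion has no arm restriction.
- **Consent (4.4, Screening and Consenting).** The consent process includes a video on handling the cap and on "how the Pillsy system works to aid in the subject's and study subject partner's understanding of this technology".
- **Order of steps (4.4).** Allocation comes next: "If the participant meets inclusion/exclusion criteria, he/she will be randomly assigned to one of the two arms of the study".
- **Helper function (Section 5, Intervention).** PLY participants can name "friends and family members who will also receive a text message notification one hour after a missed dose", so that "his or her support system can attempt to contact the patient and offer motivation". The section states that this content is for PLY and not for SAU.
- **Control arm (Section 5, Intervention and Screening Visit).** The SAU cap "will track openings but will not provide reminders or any other messaging". System training is given to those randomised to PLY; SAU is said to need none.
- **Comparison intended (Section 3).** Objective 1 compares Pillsy-delivered BUP/NAL adherence with conventional BUP/NAL therapy.

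**The concern.** A supporter who can contact the patient is one of the routes by which Section 5 expects Pillsy to work. The plan withholds the missed-dose text from SAU, but it applies two preparatory steps before the arm is known: obtaining the supporter's agreement to take part, and offering the supporter an explanation of the system. A partner who has agreed to help and has seen the video can ask about doses without receiving any text.

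If that happens, SAU is not quite the conventional therapy of Objective 1, and the between-arm difference in adherence is pulled towards zero. Phase I is meant to show that Pillsy can produce some improvement and to inform Phase II. An unrecorded dilution would make a small or null difference harder to interpret, and it would recur in Phase II if the same consent procedure were kept.

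**Working it through.** The plan gives no figure on this point, so the main check is to set the steps side by side by arm.

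| Step | PLY | SAU | Source |
|---|---|---|---|
| Names a partner who agrees to participate | yes | yes | 4.1 |
| Partner is an intended viewer of the Pillsy video | yes | yes | 4.4 |
| Random allocation | – | – | 4.4, after consent and eligibility |
| System training | yes | no | 5, Screening Visit |
| App, reminders, Helper texts | yes | no | 5, Intervention |

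The first two rows come before allocation and cannot differ by arm. The last two come after it and do. The Helper is therefore enlisted, and possibly briefed, in SAU, but not activated there.

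**Could the trial detect prompting in SAU?** Table 1 names no measure of it. The scripted screening in Section 5 documents availability of social support, but only at entry. The cap and platform log openings, missed doses, texts and calls, not who prompted a dose. The usability questionnaire is listed for weeks 1 and 12; its items are not reproduced, and nothing says that it covers partner behaviour.

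**Illustration only.** Let *s* be the share of the Pillsy effect that an enlisted, briefed partner alone gives to SAU. The documents give no value for *s*; the values below are assumptions.

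- Remaining contrast = (1 − s) × full effect.
- Relative information = (1 − s)², because required sample size varies with 1/effect² at fixed variance.
- Section 6.1 uses a 20% increase for the Phase II calculation. It is read here as 20 percentage points, which is an interpretation.

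| s (assumed) | Contrast, points | Relative information |
|---|---|---|
| 10% | 20 × 0.90 = 18 | 0.90² = 0.81 |
| 25% | 20 × 0.75 = 15 | 0.75² = 0.56 |
| 50% | 20 × 0.50 = 10 | 0.50² = 0.25 |

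**Power under further assumptions.** Take a binary adherence outcome, 40% in SAU and 60% in PLY, three assessments with within-person correlation 0.5, two-sided 5%, and no attrition. Effective n per arm = n × 3/(1 + 2 × 0.5) = 1.5n. The diluted SAU rate is 0.40 + 0.20s. Power = Φ[(d − 1.96·SE₀)/SE₁], with d the difference in proportions and SE₀, SE₁ its standard errors under the null and the alternative.

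| s (assumed) | SAU rate | 15 per arm (effective 22.5) | 100 per arm (effective 150) |
|---|---|---|---|
| 0 | 0.40 | 26% | 94% |
| 10% | 0.42 | 22% | 88% |
| 25% | 0.45 | 17% | 74% |

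At the Phase I size power is low with or without dilution. The loss would matter more at the Phase II size.

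**The case against.** **A common criterion is right.** Requiring a willing partner of everyone before allocation keeps the arms comparable on social support. This stands, and the fix keeps it. The point concerns the partner's briefing, not the criterion.

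**Consent must describe the intervention.** True for participants, who would still see the video. It does not require that the partner be briefed before allocation.

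**The trial compares packages, and the missed-dose text stays PLY-only.** Also true. The trial does not claim to isolate the social-support component. What remains is that a supporter enlisted by the study is not part of services as usual. Where the partner is a provider with a care role anyway, the added exposure may be small.

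**The trial is a 30-person proof of concept.** The power figures bear this out: dilution would change little in what a test can conclude at 15 per arm. The case for acting rests on interpretation and on Phase II.

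Three stronger readings are tempting, and the documents do not support them:

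- A reader might infer that partners must come to the consent visit. Section 4.1 asks only that one be identified who agrees; Section 4.4 says only that the video is meant to help the partner too. Nor is the video said to cover missed-dose alerts.
- A reader might infer that SAU partners will take the absence of a text to mean that a dose was taken, which would lower SAU adherence, inflate the effect and be a safety concern. Nothing suggests that SAU partners expect texts: SAU has no app, no Helper set-up and no system training.
- A reader might treat silence about the SAU partner's role as proof that nothing is said to them. The consent form is not part of the text available and may cover it.

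**Conclusion.** The point holds as a possible, avoidable and unmeasured route of contamination. The factual basis is firm: the partner criterion applies to both arms, the partner is an intended viewer of a pre-randomisation video, and Helper activation and training are PLY-only. The likely direction is dilution of the PLY–SAU contrast, assuming that some SAU partners watch or hear of the video and then prompt doses. The size cannot be derived from the documents, and the figures above show only how the contrast would respond to assumed values. This does not invalidate the trial; it is an inexpensive improvement worth making.

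**What to change.** 1. **4.1:** keep the criterion for all candidates, worded so that it asks only whether the candidate can name a willing partner.
2. **4.4:** remove the partner from the pre-randomisation video. Participants in both arms still see it.
3. **Section 5, Screening Visit:** brief partners after allocation, in PLY only, alongside the PLY training already planned there. Helper activation needs no change, since it is already PLY-only.
4. **After allocation:** tell SAU participants, and any partner already contacted, that the SAU cap sends no alerts. This also makes the SAU partner's position explicit.
5. **Table 1:** at weeks 1, 6 and 12, in both arms, record whether anyone prompted the participant to take doses, and report the answers by arm.

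**Cost.** Protocol wording, one statement to SAU participants and one question at three existing visits. A few PLY partners may decline once briefed, leaving those participants without an active Helper; Section 5 already makes naming Helpers optional. The question adds a small burden and could itself slightly suggest prompting, so it should be short, neutral and identical in both arms. If the sponsor prefers to keep partner briefing in both arms, the protocol should give the reason, state the SAU partner's role, and still record prompting by arm.

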4.2 EXCLUSION CRITERIA

Participants will be **excluded** if they:

- Have known hypersensitivity or allergy to BUP and/or NAL.
- Are pregnant or lactating women, or women of childbearing potential who are not using any form of birth control.
- Require opioids for the treatment of chronic, non-acute pain.
- Are unable to provide voluntary informed consent.
- Have pending legal issues that could adversely affect the participant's freedom to participate.
- Cannot read or speak English.

4.3 SCREENING FAILURES

Participants who do not meet one or more criteria required for participation in the study during the screening procedures, are considered screen failures. These participants will still be assigned a screening number, but we will only collect the minimal information including demography and the reason for screen failure.

Participants who did not meet the criteria to participate in this trial because of pending legal issues may be rescreened if their legal situation is resolved. All study personnel will be trained according to the Collaborative Institutional Training Initiative (CITI) and receive protocol training before starting any recruitment.

4.4 STRATEGY FOR RECRUTEMENT

Study participants will be recruited from Ideal Option outpatient treatment centers (a drug addiction treatment center) in Spokane WA, that routinely prescribes OAT. In general, patients will have received referrals from emergency departments, hospital discharge staff for opioid overdose, or law enforcement. Patients may be given up to 30 days of BUP/NAL prior to this initial referral visit. At least 30 patients between 18 and 60 years of age will be randomized to receive PLY or SAU.

Potential subjects will be identified by the outpatient clinicians, nurse managers, medical assistants and referred to the study coordinator. Patients will also see flyers in the waiting room and can self-identify and request an appointment with the coordinator. The study coordinator will assess subject eligibility and obtain informed consent. The latest version of an approved informed consent form by Washington State University IRB will be used.

Subject Characteristics and Data Collection Procedure

Only subjects who qualify for BUP/NAL treatment for OAT will be approached. Subject characteristics that will be documented include age; sex; race; employment; history of psychiatric illness; opioid of choice; years of opioid use; history of overdose; other substance use (tobacco, alcohol, cocaine, or benzodiazepines); previous addiction treatment, history of opioid medication assisted therapy. With subject permission, we will collect pertinent medical history and retrospective clinical laboratory results from the last 30 days from the patient's referring medical team and going forward during their time while enrolled in the study. This data will be collected automatically at Ideal Option and will be downloaded and connected to the research data collected. REDCap (Research Electronic Data Capture) is a data platform that ensures subject privacy and data security. This is the platform that will be used to enter research data that is collected.

Screening and Consenting

As described above the medical assistant or other clinic staff will ask whether patients would like to participate in a clinical research trial. If the patient answers yes, the patient will be

referred for follow-up with a RC. The RC will contact the patient and assess the participant's appropriateness for the study in a screening interview. The RC will explain the clinical study in detail and will obtain informed consent. All potential participants will be given plenty of time to read the consent form. They will have time to ask questions and their questions will be answered to their satisfaction by the study RC, the Principal Investigator, or the Co-investigator.

After ensuring the potential subject has understood his/her role in the study, then he/she will be requested to sign and date the Institutional Review Board (IRB) approved Informed Consent Form (ICF), after which a screening number will be assigned. The consenting process should be conducted at the clinic's site and in a consistent manner for every potential participant.

The consent process for this study will include a video demonstration of handling of the Pillsy cap and how the Pillsy system works to aid in the subject's and study subject partner's understanding of this technology. If the participant meets inclusion/exclusion criteria, he/she will be randomly assigned to one of the two arms of the study.

Method of Assigning Subjects to Study Arms: Randomization

Subjects will be centrally registered and randomly assigned 1:1 to the PLY or SAU group. We will use permuted block randomization and stratify on 1) age, 2) sex, and 3) severity of OUD (mild, moderate, severe) based on DSM-5 criteria for diagnosis of opioid use disorder (Mild: 2-3 symptoms. Moderate: 4-5 symptoms. Severe: 6 or more symptoms).

